5.1.3 Subject Exclusion Criteria

The subject must be excluded from participating in the trial if the subject:

- 1. Is currently participating and receiving study therapy or has participated in a study of an investigational agent and received study therapy or used an investigational device within 3 weeks of the first dose of treatment.
- 2. Has a diagnosis of immunodeficiency or is receiving systemic steroid therapy or any other form of immunosuppressive therapy within 7 days prior to the first dose of trial treatment. Inhaled or topical steroids are allowed.
- 3. Has a known history of active TB (Bacillus Tuberculosis).
- 4. Hypersensitivity to pembrolizumab or any of its excipients.
- 5. Has had a prior anti-cancer monoclonal antibody (mAb) within 3 weeks prior to study Day 1 or who has not recovered (i.e., ≤ Grade 1 or at baseline) from adverse events due to agents administered more than 3 weeks earlier.
- 6. Has had prior chemotherapy, targeted small molecule therapy, or radiation therapy within 2 weeks prior to study Day 1 or who has not recovered (i.e., ≤ Grade 1 or at baseline) from adverse events due to a previously administered agent.
 - Note: Subjects with ≤ Grade 2 neuropathy or alopecia are an exception to this criterion and may qualify for the study.
 - Note: If subject received major surgery, they must have recovered adequately from the toxicity and/or complications from the intervention prior to starting therapy.

- 7. Has a known additional malignancy that is progressing or requires active treatment. Exceptions include basal cell carcinoma of the skin or squamous cell carcinoma of the skin that has undergone potentially curative therapy or in situ cervical cancer.
- 8. Has known active central nervous system (CNS) metastases and/or carcinomatous meningitis. Subjects with previously treated brain metastases may participate provided they are stable (without evidence of progression by imaging for at least four weeks prior to the first dose of trial treatment and any neurologic symptoms have returned to baseline), have no evidence of new or enlarging brain metastases, and are not using steroids for at least 7 days prior to trial treatment. This exception does not include carcinomatous meningitis which is excluded regardless of clinical stability.
- 9. Has active autoimmune disease that has required systemic treatment in the past 2 years (i.e. with use of disease modifying agents, corticosteroids or immunosuppressive drugs). Replacement therapy (eg., thyroxine, insulin, or physiologic corticosteroid replacement therapy for adrenal or pituitary insufficiency, etc.) is not considered a form of systemic treatment.
- 10. Has known history of, or any evidence of active, non-infectious pneumonitis. History of radiation pneumonitis is allowed provided that it is not active and no corticosteroids were required for pneumonitis management.
- 11. Evidence of interstitial lung disease.
- 12. Has an active infection requiring systemic therapy.
- 13. Have a known immediate or delayed hypersensitivity reaction or idiosyncrasy to drugs chemically related to trametinib, or excipients or to dimethyl sulfoxide (DMSO).
- 14. History of retinal vein occlusion (RVO).
- 15. Has a history or current evidence of any condition, therapy, or laboratory abnormality that might confound the results of the trial, interfere with the subject's participation for the full duration of the trial, or is not in the best interest of the subject to participate, in the opinion of the treating investigator.
- 16. Has known psychiatric or substance abuse disorders that would interfere with cooperation with the requirements of the trial.
- 17. Is pregnant or breastfeeding, or expecting to conceive or father children within the projected duration of the trial, starting with the pre-screening or screening visit through 120 days after the last dose of trial treatment.
- 18. Has received prior therapy with an anti-PD-1, anti-PD-L1, or anti-PD-L2 agent for dose expansion. (Patients in dose escalation may have received an anti-PD-1, anti-PD-L1, or anti-PD-L2 agent).
- 19. Has a known history of Human Immunodeficiency Virus (HIV) (HIV 1/2 antibodies).
- 20. Has known active Hepatitis B (e.g., HBsAg reactive) or Hepatitis C (e.g., HCV RNA [qualitative] is detected).
- 21. History or evidence of cardiovascular risk including any of the following:

- LVEF<LLN on screening exam.
- A QT interval corrected for heart rate using the Fridericia's formula (QTcF; Appendix X) ≥470 msec (Appendix 11.2) on screening exam.
- History or evidence of current clinically significant uncontrolled arrhythmias.
- Clarification: Subjects with atrial fibrillation controlled for >30 days prior to dosing are eligible.
- History of acute coronary syndromes (including myocardial infarction and unstable angina), coronary angioplasty, or stenting within 6 months prior to enrollment.
- History or evidence of current ≥ Class II congestive heart failure as defined by New York Heart Association (NYHA; Appendix 11.5).
- Treatment refractory hypertension defined as a blood pressure of systolic> 140 mmHg and/or diastolic > 90 mm Hg which cannot be controlled by antihypertensive therapy;
- Patients with intra-cardiac defibrillators.
- 22. Has received a live vaccine within 30 days of planned start of study therapy.

Note: Seasonal influenza vaccines for injection are generally inactivated flu vaccines and are allowed; however intranasal influenza vaccines (e.g., Flu-Mist®) are live attenuated vaccines, and are not allowed.

5.2 Trial Treatments

The treatment to be used in this trial is outlined below in Table 2.

Table 2. Trial Treatments

Drug	Dose/Potency	Dose Frequency	Route of Administration	Regimen/Treatment Period	Use
Pembrolizumab (MK-3475)	200 mg	Q3W	IV infusion	Day 1 of each 3 week cycle	Experimental
Trametinib	x mg†	Daily†	PO	Daily starting D1	Experimental
† See dose escalation schema. RP2D for expansion cohorts.					

Dose Escalation Cohort (Arm A): Trametinib will be adminstered starting C1D1 and continued as per Table 3, until determination of the MTD. Pembrolizumab will be added to trametinib starting C2D1.

Dose Escalation Cohort (Arm B): Pembrolizumab will be administered starting C1D1 and trametinib will be added to pembrolizumab starting C2D1.

Expansion Cohort (Arm) A: Trametinib will be administered starting C1D1 and pembrolizumab will be added to trametinib starting C2D1 at the MTD of the combination as determined from the dose escalation portion of the study.

Expansion Cohort (Arm) B: Pembrolizumab will be administered starting C1D1 and trametinib will be added to pembrolizumab starting C2D1 at the MTD of the combination as determined from the dose escalation portion of the study.

5.2.1 Dose Selection/Modification

5.2.1.1 Dose Selection

The rationale for selection of doses to be used in this trial is provided in Section 4.0 - Background and Rationale.

The dose of pembrolizumab is fixed at 200 mg IV Q3W.

The dose escalation schema of trametinib is as follows. Each cycle is Q3W (21 days).

Table 3. Dose Escalation Schema for Trametinib

Dose Level	Trametinib dose (PO Daily) Q3W	Pembrolizumab (MK-3475) dose IV Q3W
-1	1.5 mg (D1-D7)	200 mg
*1	1.5 mg (D1-D10)	200 mg
2	2.0 mg (D1-D10)	200 mg

^{*} Dose level 1 is the starting dose. For each cohort, trametinib dose will be the same for lead in and for concurrent trametinib + pembrolizumab administration.

For Cohort A: Lead in trametinib will precede combination trametinib and pembrolizumab, which will commence for C2.

For Cohort B: Lead in pembrolizumab will precede combination trametinib and pembrolizumab, which will commence for C2.

The recommended dose expansion and recommended phase II dose (RP2D) will be determined by the overall assessment of the MTD (the maximum dose level where 6 patients have been treated in the dose escalation portion of the study) and toxicities observed in the dose escalation portion of this study.

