- Drug-related toxicity, regardless of CTCAE grade, that results in an interruption of any component of study therapy during Cycle 1 for more than 21 consecutive days and cannot be controlled within 2 weeks from its onset
- Any other Grade 2 or greater non-hematological toxicity that in the judgment of the investigator and Sponsor Investigator is dose limiting, with the exception of mild or moderate immune -mediated adverse reactions or symptomatic endocrinopathy attributable to pembrolizumab
- For Liver Function Tests
 - ALT or AST $\geq 8x$ ULN
 - ALT or AST \geq 5x ULN but \leq 8x ULN persists for \geq 2 weeks
 - ALT or AST ≥3x ULN if associated with the appearance or worsening of symptoms of hepatitis or hypersensitivity such as fatigue, nausea, vomiting, right upper quadrant pain or tenderness, pyrexia, rash or eosinophilia.

The following will NOT be considered a DLT for the purposes of this protocol:

• Clinically insignificant laboratory values of any grade (i.e. asymptomatic amylase, lipase elevations).

Dose escalation will proceed within each cohort according to the following scheme. Dose-limiting toxicity (DLT) is defined above.

The MTD is the highest dose tested in which ≤ 1 out of 6 patients has experienced a DLT.

Table 15: Dose Escalation Decision Rule Summary

Number of Patients with DLT at a Given Dose Level	Escalation Decision Rule
0 out of 3	Enter 3 patients at the next dose level.
≥2	Dose escalation will be stopped. This dose level will be declared the maximum administered dose (highest dose administered). Three (3) additional patients will be entered at the next lowest dose level if only 3 patients were treated previously at that dose.
1 out of 3	 Enter at least 3 more patients at this dose level. If 0 of these 3 patients experience DLT, proceed to the next dose level. If 1 or more of this group suffer DLT, then dose escalation is stopped, and this dose is declared the maximally administered dose. Three (3) additional patients will be entered at the next lowest dose level if only 3 patients were treated previously at that dose.
≤1 out of 6 at highest dose level below the maximum administered dose (unless ≤1 out of 6 patients have DLT's at Dose Level 2 – in which case this is also the MTD).	This is the maximum tolerated dose (MTD), and generally the recommended phase 2 dose (RP2D). At least 6 patients must be entered at the RP2D.

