8.0 STATISTICAL ANALYSIS PLAN

The initial dose escalation will follow a standard 3+3 design, starting at dose level 1. The decision to escalate to the next dose level will be determined by the rate of dose-limiting toxicity (DLT) observed during Cycle 2, with a cycle length defined as 3 weeks. Up to 3 patients will be initially enrolled in a dose cohort, starting at dose level 1. If 1 of 3 patients were to experience DLT, 3 additional patients will be enrolled at same dose level. If 0 of 3 patients or 1 of 6 patients enrolled at a dose level were to experience DLT, enrollment to next dose level will be opened. If >1 of 3 patients or >1 of 6 patients enrolled at a dose level were to experience DLT, the maximum tolerated dose (MTD) will have been exceeded. Adverse events will be collected and described for the expansion cohorts. Enrollment to dose level 1 will be expanded to 6 patients if applicable, or enrollment to dose level -1 will be opened if dose level 1 were to exceed the MTD. The highest dose level at which 0 of 3 patients or 1 of 6 patients experience DLT will be declared the MTD. A minimum of 6 patients and maximum of 18 patients will be enrolled for each cohort (Arm A: Lead in Trametinib and Arm B: Lead in Pembrolizumab) in this dose escalation portion of the study.

Enrollment into Cohorts A and B are pre-planned in regards to sequence and timing. Arm A (lead in trametinib) will open 1st to dose escalation and will accrue 3 patients. Once 3 patients are accrued for Arm A, Arm B will open and accrue 3 patients. This is to ensure cohorts remain open for accrual given the 6-week DLT period; these cohorts will alternate in opening in this fashion until the MTD is achieved for both Arm A and Arm B. Once the MTD is achieved for both Arms A and B, Arm A will open to dose expansion at the MTD and complete accrual, followed by Arm B. If one Arm is delayed in opening additional dose levels due to toxicity, the alternate cohort may open at additional dose levels if approved by the Primary Investigator in consultation with Novartis and Merck.

The recommended dose expansion and recommended phase II dose (RP2D) will be determined by the overall assessment of the MTD and toxicities observed in the study.

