All patients who receive a dose of pembrolizumab and trametinib will be analyzed for safety and efficacy. Subjects who discontinue from study participation prior to receiving the combination of trametinib and pembrolizumab will be replaced. Subjects in dose escalation who discontinue from study and are not evaluable for dose limiting toxicities will be replaced. Patients removed from study for unacceptable treatment related adverse event(s) will be followed until resolution or stabilization of all treatment related AEs to grade 2 or lower. However, they will not be replaced.

A group of 12 patients will be enrolled in each of the 2 expansion cohorts at the MTD. Patients will enroll into the next subsequent cohort upon completion of the previous cohort (Arm A then Arm B). A sequencing scheme will be considered as promising if at least 5 of 12 patients were to achieve a complete or partial response per RECIST 1.1. The decision rule is associated with 80% exact power with an exact alpha of 0.16 if the underlying response rate associated with a sequencing scheme were truly at least 50% compared to current expectation of 25% ORR with single agent pembrolizumab. A median PFS of 8 months in 12 patients per cohort will provide 81 power to detect a difference compared to historical PFS of about 4 months with single agent pembrolizumab with an alpha of 0.1 based on accrual time of 24 months and follow up of 12 months. A sequencing scheme will be recommended for further development based on a combination of promising efficacy (response rate, PFS) and favorable changes in the tumor immune microenvironment at rebiopsy, provided the safety and tolerability profiles are acceptable.

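### Section 5.2.1.1 defines the MTD by six patients treated with no DLT limit, which contradicts the at-most-1-of-6 rule in sections 5.4 and 8.0

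*Combined protocol and SAP*

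**What the plan says.** All references are to the combined protocol and SAP.

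- **5.2, Table 2 footnote**, on the trametinib dose: "See dose escalation schema. RP2D for expansion cohorts". The text below the table places each expansion arm at the MTD of the combination found in escalation.
- **5.2.1.1** bases the expansion dose and RP2D on an overall assessment of the MTD and of toxicities seen in escalation. It explains the MTD as "the maximum dose level where 6 patients have been treated in the dose escalation portion of the study".
- **5.4** runs escalation by arm: "Dose escalation will proceed within each cohort according to the following scheme". It then defines the term: "The MTD is the highest dose tested in which ≤ 1 out of 6 patients has experienced a DLT".
- **5.4, Table 15**, on the second group of three after 1 of 3 with DLT: "If 1 or more of this group suffer DLT, then dose escalation is stopped, and this dose is declared the maximally administered dose". The arm then goes to the next lower level. At least six patients must be entered at the RP2D.
- **5.4, text after Table 15**, allows an RP2D below the MTD.
- **8.0**: ">1 of 6 patients enrolled at a dose level were to experience DLT, the maximum tolerated dose (MTD) will have been exceeded". On expansion: "Once the MTD is achieved for both Arms A and B, Arm A will open to dose expansion at the MTD", followed by Arm B; and "A group of 12 patients will be enrolled in each of the 2 expansion cohorts at the MTD".
- **4.3.3 and 8.0** repeat the sentence on setting the RP2D without the parenthesis.

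**The concern.** One term has two incompatible definitions. The one in the dose-selection section counts patients treated. The one in 5.4 and 8.0 counts patients with DLT. In a 3+3 design a level often reaches six patients because the first three raised a doubt, so a headcount cannot separate a level that passed at six from one that failed at six.

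The definition carries weight because 5.2 and 8.0 place 24 expansion patients (12 per arm) at the MTD, and safety and tolerability are the primary objective. Someone who looks up the dose in the dose-selection section finds a rule that can point to a level the DLT rule has just rejected. That section gives no cross-reference to the rule that should prevail.

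**Working it through.** The plan states no figure on this point, so the check compares the texts and then asks how often the two definitions would part.

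**1. A counterexample.** At dose level 2, 1 of 3 patients has a DLT, then 1 of the next 3. Six are treated and two have DLTs.
- 5.2.1.1, read literally: level 2 is the highest level with six treated, so it is the MTD.
- 5.4: 2 of 6 is more than 1 of 6, so it is not the MTD.
- Table 15: level 2 is the maximally administered dose and the arm goes down a level.
- 8.0: the MTD has been exceeded.

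**2. Chance of that path at a single level.** With true DLT rate p, P(1 of 3) × P(at least 1 of next 3) = 3p(1−p)² × [1 − (1−p)³].
- p = 0.10: 0.243 × 0.271 = 0.066
- p = 0.20: 0.384 × 0.488 = 0.187
- p = 0.30: 0.441 × 0.657 = 0.290
- p = 0.40: 0.432 × 0.784 = 0.339

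**3. A whole arm, one case in full.** Follow Table 15: start at level 1, escalate on 0 of 3 or 1 of 6, require six at the MTD, de-escalate as far as level −1, and enrol every group of three completely. Assume DLT rates of 5%, 10% and 20% at levels −1, 1 and 2.

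Conflict at level 2:
- Level 1 is cleared for escalation: 0.729 + 0.243 × 0.729 = 0.906.
- Level 2 ends with six treated and at least two DLTs, by 1 of 3 then at least 1 of 3 (0.187) or by 0 of 3 then at least 2 of 3 (0.512 × 0.104 = 0.053). Sum 0.241.
- Product: 0.906 × 0.241 = 0.218. Almost all of these arms still end with an MTD at a lower level.

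Conflict at level 1, with level 2 never reaching six:
- 1 of 3 then at least 1 of 3: 0.243 × 0.271 = 0.0659.
- 0 of 3 at level 1, at least 2 of 3 at level 2, then at least 2 of the next 3 at level 1: 0.729 × 0.104 × 0.028 = 0.0021.
- Level −1 then passes with at most 1 of 6: 0.857 × 0.993 + 0.135 × 0.857 = 0.967.
- Product: 0.068 × 0.967 = 0.066.

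Total: 0.218 + 0.066 = 0.284.

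**4. Five assumed sets of rates.** Exact enumeration of the same rules gives the share of all arms that end with a Table 15 MTD and in which 5.2.1.1 names a higher level:

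| Assumed DLT rates, levels −1 / 1 / 2 | By 1 of 3 then ≥1 of 3 | By 0 of 3 then ≥2 of 3 | Total |
|---|---|---|---|
| 3 / 5 / 10% | 0.083 | 0.020 | 0.103 |
| 5 / 10 / 20% | 0.233 | 0.050 | 0.284 |
| 10 / 15 / 30% | 0.346 | 0.067 | 0.413 |
| 10 / 20 / 33% | 0.384 | 0.066 | 0.450 |
| 15 / 25 / 40% | 0.388 | 0.063 | 0.450 |

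Totals are rounded from unrounded parts. The path in step 1 makes up 81% to 86% of the disagreements.

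**The case against.** **The parenthesis is not the operative rule.** Section 5.4 has the defining sentence, Table 15 and 8.0 apply a DLT limit, and 4.3.3 and 8.0 give the RP2D sentence without the parenthesis. It may be meant only as a reminder of Table 15's six-patient minimum, which would have a purpose because 8.0 on its own would accept an MTD on 0 of 3. This stands as a likely account of intent, and it means that a DLT-based rule is in writing. It does not rescue the words, which define the MTD and do not add a condition to it.

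**No dose is chosen by headcount alone.** Section 5.2.1.1 also weighs observed toxicities, 5.4 lets the RP2D fall below the MTD, and 10.5 requires a meeting or call after each cohort's DLT assessment. This stands. A reader might infer that expansion patients would be treated at a rejected dose; the documents do not support that.

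**Each arm already expands at its own MTD.** A reader might take the reference to the study as a whole to pool the arms, so that one arm's MTD sets the other's expansion dose. That reading is strained: 5.4 escalates within each arm, 5.2 states the expansion dose separately for Arms A and B, 8.0 seeks an MTD for both arms before expansion, and its adverse-event paragraph speaks of the MTD for either regimen. What remains is that no sentence says so outright or addresses MTDs that differ.

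**The probabilities may be too high.** Table 15 does not say whether accrual stops at the second DLT within a group. If it did, only paths with the second DLT in the sixth patient would reach six treated. As a share of the main path at level 2 this is (1−p)²p / [1 − (1−p)³]: 0.081/0.271 = 30% at p = 0.10 and 0.144/0.784 = 18% at p = 0.40. The figures in the table therefore depend on full groups of three.

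**Conclusion.** The point holds as a conflict between definitions. The parenthesis in 5.2.1.1 is wrong as written: on an ordinary 3+3 path it labels as MTD a level that 5.4, Table 15 and 8.0 reject. Under the assumed DLT rates and full enrolment of each group of three, the definitions disagree in about 10% to 45% of arms. Lower true rates, or stopping within a group at the second DLT, would reduce this.

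The result does not measure overdosing and does not show that the arms' MTDs would be pooled. The natural reading of the rest of the document is a DLT-based MTD for each arm, with room to expand below it. The correction is worth making because the error concerns a safety-relevant dose and sits in the section where that dose is looked up.

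**What to change.** 1. In 5.2.1.1, replace the parenthesis with: *(within each arm, the highest dose level at which at most 1 of 6 patients had a DLT; see 5.4)*.
2. In 5.2 and 8.0, where expansion is placed at the MTD, write *at or below that arm's own MTD*. This makes explicit what 5.2, 5.4 and 8.0 already imply, and agrees with the allowance in 5.4 for an RP2D below the MTD.

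The cost is wording in three sections, with no added patients or procedures. The small downside is that the arms may openly expand at different trametinib doses, which limits what can be said about sequence alone.

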5.2.1.2 Dose Modification (Escalation/Titration/Other)

Adverse events (both non-serious and serious) associated with pembrolizumab exposure may represent an immunologic etiology. These adverse events may occur shortly after the first dose or several months after the last dose of treatment. Pembrolizumab must be withheld for drug-related toxicities and severe or life-threatening AEs as per Table 5 below. See dose modification and supportive care guideline sections, including use of corticosteroids. There are no dose reductions for pembrolizumab.

Dosing interruptions are permitted in the case of medical/surgical events or logistical reasons not related to study therapy (e.g., elective surgery, unrelated medical events, patient vacation, and/or holidays). Subjects should be placed back on study therapy within 3 weeks of the scheduled interruption. The reason for interruption should be documented in the patient's medical record.

Table 4. Dose Modification for Trametinib. Lowest permitted Trametinib dose will be 1.5 mg daily.

Dose Level	Trametinib Dose (QD) (D1-D10 administration unless otherwise specified)		
For Starting Dose	2 mg	1.5 mg	1.5 mg (dosed from D1-D7)
1 st Does Reduction	1.5 mg	1.5 mg (dosed from D1-D7)	Discontinue Trametinib
2 nd Dose Reduction	1.5 mg (dosed from D1-D7)	Discontinue trametinib	-

Table 5. Dose Modification Guidelines for Pembrolizumab (MK-3475) for Drug-Related Adverse Events

Toxicity	Hold Treatment For Grade	Timing for Restarting Treatment	Treatment Discontinuation
Diarrhea/Colitis	2-3	Toxicity resolves to Grade 0-1	Toxicity does not resolve within 12 weeks of last dose or inability to reduce corticosteroid to 10 mg or less of prednisone or equivalent per day within 12 weeks
	4	Permanently discontinue	Permanently discontinue
AST, ALT, or Increased	2	Toxicity resolves to Grade 0-1	Toxicity does not resolve within 12 weeks of last dose
Bilirubin	3-4	Permanently discontinue (see exception below) ^a	Permanently discontinue
Type 1 diabetes mellitus (if new onset) or	T1DM or 3-4	Hold pembrolizumab for new onset Type 1 diabetes mellitus or Grade 3-4 hyperglycemia	Resume pembrolizumab when patients are clinically and metabolically stable

Toxicity	Hold Treatment For Grade	Timing for Restarting Treatment	Treatment Discontinuation
Hyperglycemia		associated with evidence of beta cell failure	
Hypophysitis	2-4	Toxicity resolves to Grade 0-1. Therapy with pembrolizumab can be continued while endocrine replacement therapy is instituted	Toxicity does not resolve within 12 weeks of last dose or inability to reduce corticosteroid to 10 mg or less of prednisone or equivalent per day within 12 weeks
Hyperthyroidism	3	Toxicity resolves to Grade 0-1	Toxicity does not resolve within 12 weeks of last dose or inability to reduce corticosteroid to 10 mg or less of prednisone or equivalent per day within 12 weeks
	4	Permanently discontinue	Permanently discontinue
Hypothyroidism		Therapy with pembrolizumab can be continued while thyroid replacement therapy is instituted	Therapy with pembrolizumab can be continued while thyroid replacement therapy is instituted
2 ^b T Infusion		Toxicity resolves to Grade 0-1	Permanently discontinue if toxicity develops despite adequate premedication
Reaction	3-4	Permanently discontinue	Permanently discontinue
Pneumonitis	neumonitis 2 Toxicity resolves to Grade 0-1		Toxicity does not resolve within 12 weeks of last dose or inability to reduce corticosteroid to 10 mg or less of prednisone or equivalent per day within 12 weeks
	3-4	Permanently discontinue	Permanently discontinue
Nephritis or inabi		Toxicity does not resolve within 12 weeks of last dose or inability to reduce corticosteroid to 10 mg or less of prednisone or equivalent per day within 12 weeks	
	3-4	Permanently discontinue	Permanently discontinue
All Other Drug- Related Toxicity ^c	3 or Severe	Toxicity resolves to Grade 0-1	Toxicity does not resolve within 12 weeks of last dose or inability to reduce corticosteroid to 10 mg or less of prednisone or equivalent per day within 12 weeks
	4	Permanently discontinue	Permanently discontinue

Note: Permanently discontinue for any severe or Grade 3 drug-related AE that recurs or any life-threatening event.

In case toxicity does not resolve to Grade 0-1 within 12 weeks after last infusion, trial treatment should be discontinued after consultation with the Sponsor Investigator. Subjects who require corticosteroids to manage drug-related adverse events must be at an equivalent dose of ≤10mg per day of prednisone to resume dosing with pembrolizumab. Furthermore, an inability to reduce

^a For patients with liver metastasis who begin treatment with Grade 2 AST or ALT, if AST or ALT increases by greater than or equal to 50% relative to baseline and lasts for at least 1 week then patients should be discontinued.

b If symptoms resolve within one hour of stopping drug infusion, the infusion may be restarted at 50% of the original infusion rate (e.g., from 100 mL/hr to 50 mL/hr). Otherwise dosing will be held until symptoms resolve and the subject should be premedicated for the next scheduled dose; Refer to Table 3 – Infusion Treatment Guidelines for further management details.

^c Patients with intolerable or persistent Grade 2 drug-related AE may hold study medication at physician discretion. Permanently discontinue study drug for persistent Grade 2 adverse reactions for which treatment with study drug has been held, that do not recover to Grade 0-1 within 12 weeks of the last dose.

the corticosteroid dose for managing a drug-related adverse event to the equivalent of \leq 10 mg prednisone per day within 12 weeks of last pembrolizumab dose should result in permanent discontinuation from pembrolizumab. With investigator and Sponsor Investigator agreement, subjects with a laboratory adverse event still at Grade 2 after 12 weeks may continue treatment in the trial only if asymptomatic and controlled. For information on the management of adverse events, see Section 5.7.2.

In subjects who continue on pembrolizumab having experienced a Grade 3, Grade 4, or persistent (> 4 weeks) Grade 2 drug-related AE, once the subject has recovered from the AE to Grade 0-1, the dosing interval in subsequent cycles may be increased by 1 week (e.g., to every 4 week dosing in subjects who were on an every 3 week schedule). However, in subjects who experience Grade 3 or 4 pneumonitis, or recurrent persistent (>4 weeks) Grade 2 drug - related pneumonitis after rechallenge from a prior episode of persistent (> 4 weeks) Grade 2 drug-related pneumonitis, pembrolizumab must be permanently discontinued.

For subjects who experience a recurrence of the same AE(s) at the same grade or greater with rechallenge of pembrolizumab, a consultation between the Sponsor Investigator and investigator should occur to determine whether the subject should continue in the trial. However, for a subject who experiences a recurrence of the same serious adverse event at the same grade or greater with rechallenge of pembrolizumab, the subject must discontinue pembrolizumab.

Table 6 Dose Modification Guidelines for Trametinib for Drug-Related Adverse Events (Unless Otherwise Specified)

Grade (CTC-AE)*	Dose Modifications
Grade 1 or Grade 2 (Tolerable)	Continue treatment and monitor as clinically indicated.
Grade 2 (Intolerable) or Grade 3	Interrupt therapy until toxicity is grade 0-1 and reduce by one dose level when resuming therapy.
Grade 4	Discontinue permanently, or interrupt therapy until Grade 0 to 1 and reduce by one dose level when resuming therapy.

Please follow Table 5 and Table 6 for dose modifications unless specified below.

For Grade \geq 3 drug related adverse events attributed to trametinib both pembrolizumab and trametinib should be simultaneously interrupted with the exceptions shown below.

Except for Grade ≥ 3 lymphopenia

Exceptions where dose modifications are necessary for only trametinib:

- LVEF reduction
- Retinal Vein Occlusion (RVO) and Retinal Pigment Epithelial Detachment (RPED)

Table 7. Trametinib Dose Modification Guidelines and Stopping Criteria for LVEF Decrease

Clinical Evaluation	LVEF-drop (%) or CTCAE grade	Action and Dose Modification
Asymptomatic	Absolute decrease of >10% in LVEF compared to baseline and ejection fraction below the institution's LLN.	 Interrupt trametinib and repeat ECHO/MUGA within 2 weeks.^a If the LVEF recovers within 4 weeks (defined as LVEF ≥LLN and absolute decrease ≤10% compared to baseline): Consult with the Novartis trametinib medical monitor and request approval for restart. Restart treatment with trametinib at reduced dose by one dose level. Repeat ECHO/MUGA 2, 4, 8, and 12 weeks after restart; continue in intervals of 12 weeks thereafter. If LVEF does not recover within 4 weeks: Consult with cardiologist. Permanently discontinue trametinib. Report as SAE Repeat ECHO after 2, 4, 8, 12, and 16 weeks or until resolution.
Symptomatic ^b	 Grade 3: resting LVEF 39-20% or >20% absolute reduction from baseline Grade 4: Resting LVEF ≤20%. 	 Permanently discontinue trametinib. Report as SAE. Consult with cardiologist. Repeat ECHO/MUGA after 2, 4, 8, 12, and 16 weeks or until resolution.

^a If ECHO/MUGA does not show LVEF recovery after 2 weeks, repeat ECHO/MUGA 2 weeks later.

^b Symptoms may include: dyspnea, orthopenea, and other signs and symptoms of pulmonary congestion and edema.

Table 8. Trametinib Withholding and Stopping Criteria for QTc Prolongation

Prolongation*	Action and Dose Modification
 QTc ≥501 msec, or Uncorrected QT >600 msec, or QTc >530 msec for subjects with bundle branch block 	 Interrupt study treatment until QTc prolongation resolves to grade 1 or baseline. Test serum potassium, calcium, phosphorus, and magnesium. If abnormal, correct per routine clinical practice to within normal limits. If the QTc prolongation resolves to grade 1 or baseline, trametinib may be resumed if the investigator and study chair agree that the subject will benefit from further treatment. If the event does not resolve, permanently discontinue study treatment. If the event recurs, permanently discontinue study treatment.

Abbreviations: msec = milliseconds; QTc = QT interval on electrocardiogram

 Table 9. Trametinib Dose Modification Guidelines for Hypertension

Toxicity Grade	Dose Modification	
2: Asymptomatic	Maintain dose level	
3: Asymptomatic	Hold until blood pressure is well controlled. Restart at reduced dose level.	
3: Symptomatic	Hold until blood pressure is well controlled. Restart at reduced dose level.	
4	Permanent discontinuation of treatment.	

Eye Disorders

Visual changes have been observed in patients receiving trametinib, and can be caused by central serous retinopathy (CSR) with retinal pigment epithelial detachments (RPED), or Retinal Vein Occlusion (RVO). Patients are required to have a standard ophthalmic exam performed by an ophthalmologist at baseline and any time patients report visual disturbance. The exam will include indirect fundoscopic examination, visual acuity (corrected), visual field examination, tonometry, and direct fundoscopy. Special attention should be given to retinal (e.g., CSR, RPED) or retinal vein abnormalities (e.g., RVO).

^{*} Based on average QTcF value of triplicate ECGs. For example, if an ECG demonstrates a prolonged QT interval, obtain two or more ECGs over a brief period, and then use the averaged QTcF values of the three ECGs to determine if study treatments should be interrupted or discontinued. (See Appendix 11.4 for QTcF calculation).

Table 10. Management and Trametinib Dose Modification for Visual Changes and/or Ophthalmic Examination Findings

Event CTCAE Grade	Management Guideline	Dose Modification
Grade 1*	Consult ophthalmologist within 7 days of onset.	 If dilated fundus examination cannot be performed within 7 days of onset, hold trametinib until RPED and RVO can be excluded by retina specialist/ophthalmologist. If RPED and RVO excluded, continue/or restart trametinib at same dose level. If RPED suspected/diagnosed: See RPED dose modification table below (following this table); report as SAE. If RVO diagnosed: Permanently discontinue trametinib and report as SAE.
Grade 2 and Grade 3	Consult ophthalmologist immediately.	 Hold trametinib If RPED or RVO excluded, restart trametinib at same dose level after visual AE is ≤ grade 1. If no recovery within 3 weeks, discontinue trametinib If RPED diagnosed: See RPED dose modification table below; report as SAE. If RVO: Permanently discontinue trametinib and report as SAE.
Grade 4	 Consult ophthalmologist immediately. Report as SAE. 	 Hold Trametinib If RPED/RVO excluded, may restart trametinib at same or reduced dose after discussion with the Principal Investigator If RVO or RPED, permanently discontinue trametinib.

Abbreviations: RPED=retinal pigment epithelial detachments; RVO=retinal vein occlusion; SAE=serious adverse event

* If visual changes are clearly unrelated to study treatment (e.g., allergic conjunctivitis), monitor closely but ophthalmic examination is notrequired.

Table 11. Trametinib Dose Modification for RPED

Event CTCAE Grade	Action and Dose Modification
Grade 1 RPED (Asymptomatic; clinical or diagnostic observations only)	Continue treatment with retinal evaluation monthly until resolution. If RPED worsens, follow instructions below.
Grade 2-3 RPED (Symptomatic with mild to moderate decrease in visual acuity; limiting instrumental ADL)	 Interrupt trametinib. Retinal evaluation monthly. If improved to ≤ Grade 1, restart trametinib with one dose level reduction (reduced by 0.5 mg) or discontinue in patients taking trametinib 1 mg daily. If no recovery within 4 weeks permanently discontinue trametinib

Table 12. Management and Dose Modification Guidelines for Diarrhea

CTCAE Grade	Adverse Event Management	Action and Dose Modification
Uncomplicated Diarrhea, ¹ Grade 1 or 2	 Diet: Stop all lactose containing products; eat small meals, BRAT-diet (banana, rice, apples, toast) recommended. Hydration: 8-10 large glasses of clear liquids per day (e.g., Gatorade or broth). Loperamide³: Initially 4 mg, followed by 2 mg every 4 hours or after every unformed stool; maximum 16 mg/day. Continue until diarrhea- free for 12 hours. Diarrhea >24 hours: Loperamide 2 mg every 2 hours; maximum 16 mg/day. Consider adding oral antibiotics. Diarrhea >48 hours: Loperamide 2 mg every 2 hours; maximum 16 mg/day. Add budesonide or other second-line therapies (otreotide, or tincture of opium) and oral antibiotics. 	 Continue trametinib. If diarrhea is grade 2 for > 48h, interrupt trametinib until diarrhea resolves to grade ≤1. Restart trametinib at the same dose level If treatment delay is > 28 days, discontinue trametinib.
Uncomplicated Diarrhea, ¹ Grade 3 or 4 Any Complicated Diarrhea2	 Clinical evaluation mandatory. Loperamide³: Initially 4 mg, followed by 2 mg every 4 hours or after every unformed stool; maximum 16 mg/day. Continue until diarrhea- free for 12 hours. Oral antibiotics and second-line therapies if clinically indicated Hydration: Intravenous fluids if clinically indicated. Antibiotics (oral or intravenous) if clinically indicated. Intervention should be continued until the subject is diarrhea-free for ≥24 hours. Intervention may require hospitalization for subjects at risk of life- threatening complications. 	 Interrupt trametinib and pembrolizumab until diarrhea resolves to ≤ grade 1. Then restart pembrolizumab and trametinib reduced by one dose level.⁴ If 3 dose reductions of study treatment are clinically indicated, permanently discontinue trametinib. If treatment delay is >28 days, discontinue trametinib and pembrolizumab.

¹ Uncomplicated diarrhea defined by the absence of symptoms such as cramping, nausea/vomiting, ≥ grade 2, decreased performance status, pyrexia, sepsis, neutropenia ≥ grade 3, frank bleeding, and/or dehydration requiring intravenous fluid substitution

